10.3 Efficacy Assessments

With the exception of OS, all efficacy endpoints in this trial (including the primary endpoint in Phase 2) are linked to the tumor response assessments and therefore the importance of timely and complete disease assessments in this study cannot be understated. Failure to perform any of the required disease assessments will result in the inability to determine disease status for that time point. Frequent off schedule or incomplete disease assessments have the potential to weaken the conclusion of this clinical trial.

The schedule of tumor burden assessments should be fixed according to the calendar, regardless of treatment interruptions. Tumor burden assessments will be performed until progressive disease as per RECIST 1.1 and irRECIST regardless of the discontinuation of study treatment or the start of a subsequent anticancer therapy. Patients with radiographic progression only, as defined by RECIST 1.1 should continue on study treatment until unequivocal progressive disease is determined as defined by irRECIST, at the discretion of the investigator.

The same method of assessment and the same technique used for study screening (CT scan or MRI) to characterize each lesion must be used at each subsequent post-screening assessment. Post-screening scans and the corresponding overall tumor assessment (according to RECIST and irRECIST) should be done at the next visit after the scans are performed and prior to indicating the subsequent cycle, to rule out progressive disease that would warrant study treatment discontinuation.

10.3.1 Tumor Measurements and Disease Response Assessment

10.3.1.1 Tumor Measurement and Assessment

Initial tumor imaging at screening must be performed within 28 days prior to initial study drug dosing (C1D1). (Scans performed as part of routine clinical management are acceptable for use as initial tumor imaging if they are of diagnostic quality and performed within 28 days prior to C1D1 and can be assessed by the central imaging vendor.) Patients will have radiological disease assessments performed every 6 weeks (+/-3 days) (Week 6, Week 12, etc.) during study treatment through week 36 or until progressive disease. If progressive disease has not

occurred by week 36, radiological assessments will be then be done every 9 weeks (+/-3 days) until progressive disease. If a patient comes off study for reasons other than progressive disease, radiological assessments will continue on this same study schedule until progressive disease is unequivocally documented. Images should be kept to the calendar schedule and not be delayed for delays in cycles or study drug administration. Disease response in target and non-target lesions will be assessed locally by the Investigator using RECIST 1.1 and irRECIST.

Measurable Disease

To be eligible for study participation, all patients must have documented measurable disease per RECIST 1.1 that has been radiologically documented within 28 days prior to initiating study drug treatment, defined as follows:

At least 1 measurable lesion:

- ≥ 10 mm in longest diameter on an axial image by CT scan or MRI with ≤ 5 mm reconstruction interval
 - If slice thickness is greater than 5 mm, longest diameter must be at least 2 times the thickness
- ≥ 20 mm longest diameter by chest X-ray (if clearly defined and surrounded by aerated lung); CT is preferred, even without contrast.
- Lymph nodes ≥ 15 mm in short axis on CT scan (CT slice thickness of ≤ 5 mm)

If there is only 1 measurable lesion and it is located in previously irradiated field, it must have demonstrated progression according to RECIST 1.1.

Non-measurable Lesions

Non-measurable lesions are defined per RECIST 1.1 as the following and should be captured and followed accordingly and within the eCRF according the eCRF guidelines.

- Masses < 10 mm
- Lymph nodes ≥ 10 to < 15 mm in short axis
- Leptomeningeal disease
- Ascites, pleural or pericardial effusion
- Inflammatory breast disease (cont'd on next page)
- Lymphangitic involvement of skin or lung

- Abdominal masses or organomegaly identified by physical exam which cannot be measured by reproducible imaging techniques
- Blastic bone lesions
- Both benign and equivocal (“cannot exclude”) findings should not be included

Target versus non-target

- Target: all measurable lesions up to a maximum of 2 lesions per organ and 5 lesions in total, representative of all involved organs, are to be identified as target lesions and measured and recorded at screening. Target lesions are to be selected on the basis of their size (i.e., those with the longest diameter) and suitability for accurate repeated measurement. The sum of the diameters for all target lesions is to be calculated and recorded on the eCRF as the sum of the longest diameters.
- Non-target: all other lesions not classified as target lesions (or sites of disease) are to be identified as non-target lesions and are to be recorded on the eCRF. Measurement of non-target lesions is not required.

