13.5.8 Correlative Analyses

Immune correlate values will be summarized in a descriptive manner. For immune correlates measured on a continuous scale, the number of patients with no missing data, mean, either the standard error or standard deviation, median, 25th percentile (first quartile), 75th percentile (third quartile), minimum, and maximum values will be presented. For discrete data, the frequency and percent distribution will be presented. The Wilcoxon signed rank test (for within-treatment comparisons) and Wilcoxon rank sum test (for between-treatment comparisons) will be used to identify any systematic changes in biomarker levels from baseline. Additionally, the correlation among the various initial immune correlate values may be assessed by calculating Spearman's correlation coefficient. Analysis of covariance models may be used to explore the relationship between changes in immune correlates and selected measures of antineoplastic activity (e.g., maximum change from baseline in the sum of product diameters in measurable lesions). The association among the various immune correlates and clinical outcomes (data permitting) may be explored using heat map and other data visualization techniques.

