17.4 Appendix 4: Immune-related Response Criteria Derived from RECIST 1.1 (irRECIST)

Increasing clinical experience indicates that traditional response criteria may not be sufficient to fully characterize activity in this new era of targeted therapies and/or biologics. This is particularly true for immunotherapeutic agents such as anti-CTLA-4 and anti-PD1\anti PDL1 which exert the antitumor activity by augmenting activation and proliferation of T cells, thus leading to tumor infiltration by T cells and tumor regression rather than direct cytotoxic effects (Hoos 2010; Hodi 2008). Clinical observations of patients with advanced melanoma treated with ipilimumab, for example, suggested that conventional response assessment criteria such as RECIST and WHO criteria are not sufficient to fully characterize patterns of tumor response to immunotherapy because tumors treated with immunotherapeutic agents may show additional response patterns that are not described in these conventional criteria (Hoos 2010; Nishino 2014).

Furthermore, the conventional tumor assessment criteria (RECIST and WHO criteria) have been reported as not capturing the existence of a subset of patients who have an OS similar to those who have experienced CR or PR but were flagged as PD by WHO criteria (Hoos 2010; Nishino 2012).

On these grounds, a tumor assessment system has been developed that incorporates these delayed or flare-type responses into the RECIST 1.1 criteria (irRECIST; Nishino 2014).

Lesion measurability and baseline selection of lesions:

The RECIST 1.1 definitions for measurable and non-measurable lesions apply. At baseline, all tumor lesions/lymph nodes will be categorized as measurable or non-measurable. For target lesions, a Total Measured Tumor Burden (TMTB) for all target lesions will be calculated and reported as the baseline TMTB (similarly to the Sum of Diameters in RECIST 1.1). The baseline TMTB will be used as reference to further characterize any objective tumor response in the measurable dimension of the disease.

New lesions:

irRECIST do not necessarily score the appearance of new lesions as progressive disease. Also, new lesions should be categorized as measurable or non-measurable (same measurability rules as RECIST 1.1. apply).

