In order to be selected as new measurable lesions (≤ 2 lesions per organ, ≤ 5 lesions total, per timepoint), new lesions must meet criteria as defined for baseline target lesion selection and meet the same minimum size requirements of 10 mm in long diameter and minimum 15 mm in short axis for new measurable lymph nodes. New measurable lesions shall be prioritized according to size, and the largest lesions shall be selected as new measured lesions.

All new lesions not selected as New Measurable lesions are considered New Non-measurable lesions and are followed qualitatively.

Post baseline tumor assessments:

- TMTB: At each post-baseline assessment the TMTB is defined as the sum of:
 - o Longest diameters of all non-nodal target lesions
 - o Longest diameters of all NEW non-nodal measurable lesions
 - o Short axis of all nodal target lesions
 - o Short axis of all NEW nodal measurable lesions
- Non-target lesions/New Non-measurable lesions: the RECIST 1.1 definitions for the assessment of non-target lesions apply (irCR; irNN, irPD).

Overall response at each time point:

- Immune-related complete response (irCR): Complete disappearance of all lesions (whether measurable or not) and no new lesions. All measurable lymph nodes also must have a reduction in short axis to <10 mm.
- Immune-related partial response (irPR): Decrease of $\geq 30\%$ in TMTB relative to baseline, non-target lesions are irNN, and no unequivocal progression of new non-measurable lesions
- Immune-related stable disease (irSD): Failure to meet criteria for irCR or irPR in the absence of irPD.
- Immune-related progressive disease (irPD): Minimum 20% increase and minimum 5 mm absolute increase in TMTB compared to nadir, or irPD for non-target or new non-measurable lesions.
- irNE (Not evaluable): used in exceptional cases where insufficient data exists.

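### Protocol 10.3.1.1 records the RECIST target-lesion sum by longest diameter for every target, nodes included, while Appendix 4 uses the short axis for nodes, so response or progression can be misclassified in either direction

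*Protocol*

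**What the plan says.** Protocol 10.3.1.1 makes a node measurable by its short axis: "Lymph nodes ≥ 15 mm in short axis on CT scan". All measurable lesions, up to two per organ and five in total, become targets, so nodes can enter the sum. The same section then instructs that the sum over all target lesions be "calculated and recorded on the eCRF as the sum of the longest diameters". No separate rule is given for nodes.

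Appendix 4 (17.4) treats the two kinds of lesion differently. Its total measured tumor burden (TMTB) takes longest diameters for non-nodal targets and, for nodes, "Short axis of all nodal target lesions". It presents the sum for target lesions as the "baseline TMTB (similarly to the Sum of Diameters in RECIST 1.1", which makes the two sums analogues. It also requires a nodal short axis below 10 mm for irCR.

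The primary endpoint is PFS by the local investigator using RECIST 1.1 (SAP 4.2.1). Protocol 10.3.1.1 has the investigator assess response by both RECIST 1.1 and irRECIST, and 10.3.1.3 leaves progression to the site and not to the core laboratory. The SAP gives no measurement rule.

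**The concern.** Read literally, the protocol asks a site to measure one node at one visit by its long axis for the RECIST sum and by its short axis for TMTB. The long axis gives the node more weight in the sum, and the two axes need not change together. The same scan can therefore fall on different sides of a response or progression threshold.

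The RECIST assessment carries the primary endpoint and RECIST-based ORR and CBR. Protocol 6.2 allows up to about 50 centers, so practice may also vary between sites.

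The comparison between criteria is at stake too. In a patient with no new lesions, TMTB and a RECIST sum measured on the same axes would be the same number. If the axes differ, a RECIST versus irRECIST difference may come from the measurement and not from the response pattern. SAP 11.3 plans waterfall and spider plots under both criteria, and plots of tumor change would draw on recorded measurements whatever category the investigator assigned.

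**Working it through.** **Plan's own figure.** The plan states none on this point. The conflict is textual, and the arithmetic below only shows what it can do.

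**Inputs.** Lesion sizes are assumed, because the documents give none. Thresholds are those printed in Appendix 4: progression at +20% with at least +5 mm, partial response at -30%. I apply them to both sums because the protocol does not print the RECIST 1.1 thresholds. Baseline is taken as nadir.

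**Formulas.** Let n be the non-nodal longest diameter, and L and S the node's long and short axes.
- Change on the 10.3.1.1 sum = (n1 + L1)/(n0 + L0) - 1
- Change on the Appendix 4 sum = (n1 + S1)/(n0 + S0) - 1

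**Results (mm).**

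| Case | Non-nodal | Node, L x S | Long-axis sum | Short-axis sum |
|---|---|---|---|---|
| A | 20 to 28 | 34x16, unchanged | 54 to 62, +14.8%, stable | 36 to 44, +22.2% and +8, PD |
| B | 20 to 21 | 24x18 to 32x19 | 44 to 53, +20.5% and +9, PD | 38 to 40, +5.3%, stable |
| C | 20 to 15 | 34x16 to 28x9 | 54 to 43, -20.4%, stable | 36 to 24, -33.3%, PR |
| D | 20, unchanged | 34x16 to 17x8 | 54 to 37, -31.5%, PR | 36 to 28, -22.2%, stable |
| E | 20 to 16 | 24x16 to 19.2x12.8 | 44 to 35.2, -20.0%, stable | 36 to 28.8, -20.0%, stable |

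A and B move progression in opposite directions, and C and D do the same for response. In E every lesion changes in proportion and the sums agree. A and D need no change in nodal shape: they arise because the node is 34/54 = 63% of one baseline sum and 16/36 = 44% of the other.

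**Sensitivity of the examples.** With a 24x16 node in case A, the long-axis sum goes 44 to 52 (+18.2%), still stable against PD. If the non-nodal lesion reaches 29 instead of 28, both sums give PD (44 to 53, +20.5%; 36 to 45, +25.0%). In case C, if the node shrinks in proportion (L = 34 x 9/16 = 19.125), the long-axis sum goes 54 to 34.125 (-36.8%) and both give PR.

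**Simulation, all inputs assumed.** Each simulated patient had one follow-up against baseline. Inputs were a non-nodal lesion of 15 to 60 mm, nodal short axis 15 to 30 mm, long/short ratio 1.2 to 2, and SD of log change 0.35. As the correlation between short- and long-axis change fell from 1.0 to 0.5, the share of assessments with a different category rose from 3.9% to 20.3% with one node plus one other target. With a node as the only target it rose from 2.6% to 44.5%. These figures describe the assumptions and not this trial.

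**Design figures.** At HR 0.57, one-sided 0.1 and 80% power, the Schoenfeld formula gives 4(1.2816 + 0.8416)²/(ln 0.57)² = 57.1, so 58 events. For a fixed design, the planned 60 events give 81.5% power. The measuring rule does not enter this calculation.

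**The case against.** The strongest reply is that the endpoint is the investigator's RECIST 1.1 judgement. Nothing in either document derives the category by program from the eCRF sum, and SAP 6.2 has overall response determined locally by the investigator. An investigator who applies RECIST 1.1 as named may not follow the literal wording for nodes, the phrase may be little more than a field label, and the eCRF guidelines that 10.3.1.1 mentions are not available here. This stands, and it limits the point to a risk. It does not remove the conflict: 10.3.1.1 is the only place in the documents that says how the RECIST sum is formed, and a site using the short axis for its judgement could still record a sum that does not support its own category.

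A reader might infer that progression is systematically delayed. Case B shows the reverse and case E no difference. A reader might also set a one-scan delay of 6 weeks against the hypothesized 3-month gain in median PFS. That compares one hypothetical patient with a between-arm difference, and a delay in both arms does not subtract from the gain. Progression through non-target disease and death do not depend on the sum.

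Under 10.3.1.3 the core laboratory reviews investigator-called responses, holds all scans in case the sponsor wants PFS outcomes confirmed, and may read non-responders. This mitigates in part: progression is not routinely checked, and neither are missed responses.

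Protocol 13.5.8 mentions a sum of product diameters. It is only an example in an optional exploratory analysis that SAP 10.12 defers to a separate document, so it adds nothing here.

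**Conclusion.** The inconsistency is real and unreconciled: literal use of 10.3.1.1 puts nodal targets on a different axis from Appendix 4. Three conditions are needed before a category changes: the patient has a nodal target, the site follows the literal wording, and the two sums fall on different sides of a threshold. Response and progression can then be misclassified in either direction, and RECIST versus irRECIST differences may partly reflect the axis.

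The documents do not support saying that outcomes are misclassified. They also do not support any count of affected patients, because they give neither the share with nodal targets nor any axis data. The net effect on PFS or ORR cannot be calculated. With entinostat and placebo blinded, the error is likely to be largely non-differential noise. Planned events and power are unchanged. The correction is worth making because it is cheap and concerns a locally assessed primary endpoint.

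**What to change.** In 10.3.1.1 and the eCRF guidelines, state that the sum of diameters uses the longest diameter for non-nodal targets and the short axis for nodal targets, as in Appendix 4, and name the eCRF field accordingly. For any nodal target already recorded, check which axis was used and re-measure from existing scans where needed. Under 10.3.1.3 these scans are held by the core laboratory, so no new imaging is required. The cost is one sentence in each document, with a small amount of data checking and re-measurement.

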10.3.1.2 Scan Procedures

Contrast-enhanced CT scans of chest, abdomen, and, as clinically indicated, pelvis are preferred for evaluation of disease status for this study; however, a contrast-enhanced MRI can also be performed if a patient has or develops allergy to iodinated contrast agents. The imaging modality used at screening should continue for all images during study participation, unless clinically contra-indicated.

Positron emission tomography (PET) alone will not be acceptable as part of the imaging to be performed for this study. If PET is performed, the Investigator should not remove any patient based on PET alone, as there can be false positives. If he/she thinks a patient has progressed via PET, it must be confirmed with a CT/MRI.

If a combined 18F-deoxyglucose (FDG) PET-CT scan is performed, the CT portion of that examination should not be substituted for the dedicated CT examinations required by this protocol for tumor measurements **unless** the study center can document that the CT performed as part of the FDG PET-CT is of identical diagnostic quality to a diagnostic CT (with IV and oral contrast).

CT Scan Procedures

Study centers must acquire and submit CT scans according to the parameters below:

- Use consistent scan parameters (spacing, thickness, field of view, etc.) for all assessments. Any alternate imaging or parameter variation from the protocol should be noted.
- If a patient develops hypersensitivity to the iodinated contrast medium while on study, it is acceptable to perform chest CT scans without contrast. In addition, a contrast-enhanced MRI scan according to the parameters described in the MRI section must be performed for the remainder of the required anatomy.
- The patient should be given oral contrast (as either positive [e.g., barium or Gastrograffin] or negative [e.g., water or saline] contrast media, according to site standard of care) prior to the examination to allow for sufficient bowel opacification.
- Non-ionic iodinated IV contrast with a minimum of 320 mg iodine/mL should be used for this study. Contrast agent volume should be according to the package insert. The same contrast agent with the same concentration should be used throughout the study.

MRI Scan Procedures

- If IV contrast is medically contraindicated during the study, a dynamic contrast-enhanced MRI is an acceptable alternative to CT scans of the abdomen and pelvis.
- MRI must be performed using either 1.5T or 3.0T scanner. A change in scanner field strength is not allowed for an individual patient while on study (e.g., if a patient has a C2 MRI scan at 3.0T, all subsequent scans must be performed at 3.0T).
- MRI scans should use optimized parameters to decrease motion artifact and maximize signal-to-noise ratio and resolution. Breath-hold imaging, fast-scanning techniques, and gadolinium should be used to maximize lesion identification. Note: A non-contrast CT scan of the chest or digital chest X-ray must be acquired in addition to the MRI of the abdomen and, as applicable, pelvis.
- The patient must undergo scanning with approved extracellular contrast media only (e.g., Magnevist, Dataram, Omnipaque).

- The same equipment, field strength, sequences, scanning parameters, positioning, angulation, timing, field of view, and slice thickness should be utilized for all examinations acquired both pre- and post-contrast for a given patient over the course of the study.

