9.12 Prohibited Medication

The following medications are excluded while the patient is receiving study treatment:

- Any other HDAC inhibitor, including valproic acid
- DNA methyltransferase inhibitors
- Any additional investigational or commercial anticancer agents, such as chemotherapy, immunotherapy, targeted therapy, biological response modifiers, or endocrine therapy, will not be allowed, even if utilized as treatment of non-cancer indications.
- Prophylactic use of hematopoietic colony stimulating factors are not allowed during the Phase 1b, but can be used per investigator discretion during other parts of the study.
- Radiation therapy

Note: Radiation therapy to a symptomatic solitary lesion or to the brain may be considered on an exceptional case-by-case basis after consultation with the Medical Monitor. The radiation field cannot encompass a target lesion. Radiation to a target lesion is considered progressive disease and the subject should be removed from study treatment. The patient must have clear measurable disease outside the radiated field. Administration of palliative radiation therapy will be considered clinical progression.

- Traditional herbal medicines; these therapies are not fully studied and their use may result in unanticipated drug-drug interactions that may cause or confound the assessment of toxicity
- RANKL inhibitor (denosumab): patients who are receiving denosumab prior to randomization must be willing and eligible to receive a bisphosphonate instead while on study
- Immunomodulatory agents, including but not limited to interferons or IL-2, during the entire study; these agents could potentially increase the risk for autoimmune conditions when received in combination with atezolizumab
- Immunosuppressive medications, including but not limited to cyclophosphamide, azathioprine, methotrexate, and thalidomide; these agents could potentially alter the activity and the safety of atezolizumab
- Use of steroids to premedicate patients for whom CT scans with contrast are contraindicated (i.e., patients with contrast allergy or impaired renal clearance); in such patients, MRIs of the chest, abdomen, and pelvis with a non-contrast CT scan of the chest must be performed
- Any live, attenuated vaccine (e.g., FluMist®) while the patient is receiving atezolizumab and for a period of 90 days after the discontinuation of atezolizumab

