9.14.1 Pulmonary Events

Dyspnea, cough, fatigue, hypoxia, pneumonitis, and pulmonary infiltrates have been associated with the administration of atezolizumab.. Patients will be assessed for pulmonary signs and symptoms throughout the study and will also have CT scans of the chest performed at every tumor assessment.

All pulmonary events should be evaluated thoroughly for other commonly reported etiologies such as pneumonia/infection, lymphangitic carcinomatosis, pulmonary embolism, heart failure, chronic obstructive pulmonary disease, or pulmonary hypertension. by the following means:

Measurement of oxygen saturation (i.e., arterial blood gas)

Bronchoscopy with bronchoalveolar lavage and biopsy

Pulmonary function tests (diffusion capacity of the lung for carbon monoxide [DL_{CO}])

Pulmonary function testing with a pulmonary embolism protocol

Table 9-3 Management Guidelines for Pulmonary Events, Including Pneumonitis

Severity	Management
Grade 1	
Continue atezolizumab with close monitoringRe-evaluate on serial imagingConsider pulmonary consultation
Grade 2	
Withhold atezolizumab for up to 12 weeks after event onset.^aPulmonary and infectious disease specialists consultation and consider bronchoscopy or bronchoscopic alveolar lavage (BAL)Start treatment with 1–2 mg/kg/day oral prednisone or equivalentWhen improves to Grade 0 or Grade 1, then taper steroids over ≥ 1 month. Atezolizumab may be resumed if the event improves to Grade 0 or Grade 1^bIf event does not resolve to Grade 1 or better while withholding atezolizumab, permanently discontinue atezolizumab and contact Medical Monitor^cTreat as Grades 3–4 for recurrent events
Grades 3–4	
Permanently discontinue atezolizumab and contact Medical Monitor^cBronchoscopy/BAL is recommendedStart treatment with 1–2 mg/kg/day oral prednisone or equivalentTaper steroids over ≥ 1 month after symptoms improve to Grade 0 or Grade 1If not improving within 48 hours after initiating corticosteroids, consider adding an immunosuppressive agent

^a Atezolizumab may be withheld for a longer period of time (i.e., > 12 weeks after event onset) to allow for corticosteroids (if started) to be reduced to ≤ 10 mg/day oral prednisone or equivalent. The acceptable length of the extended period of time must be agreed upon by the investigator and the Medical Monitor.

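### Section 10.3.1.2 lets patients imaged by MRI have a chest X-ray instead of a non-contrast chest CT, against Sections 9.12 and 9.14.1; lung lesions of 10–19 mm are then not measurable and lung progression may be found later

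*Protocol*

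**What the plan says.** Four places in the protocol deal with chest imaging when iodinated contrast cannot be used, or with chest imaging in general.

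- **Section 10.3.1.2, MRI Scan Procedures.** A note to the MRI rules says "A non-contrast CT scan of the chest or digital chest X-ray must be acquired in addition to the MRI of the abdomen". CT and X-ray are offered as equal alternatives, with no condition on when X-ray may be chosen.
- **Section 9.12.** Steroid premedication for contrast CT is prohibited when contrast CT is contraindicated (contrast allergy or impaired renal clearance). The section continues: "in such patients, MRIs of the chest, abdomen, and pelvis with a non-contrast CT scan of the chest must be performed".
- **Section 9.14.1.** As part of pulmonary monitoring, patients "will also have CT scans of the chest performed at every tumor assessment".
- **Section 10.3.1.2, CT Scan Procedures.** For hypersensitivity to contrast that develops on study, "it is acceptable to perform chest CT scans without contrast", with contrast-enhanced MRI for the rest of the anatomy. X-ray is not mentioned.

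Section 10.3.1.1 defines measurable disease. By CT or MRI the minimum is "10 mm in longest diameter on an axial image by CT scan or MRI with" a reconstruction interval of at most 5 mm. By plain film it is "20 mm longest diameter by chest X-ray (if clearly defined and surrounded by aerated lung); CT is preferred, even without contrast".

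The primary endpoint is PFS by RECIST 1.1 as assessed by the investigator. SAP Table 1 dates progression at the first disease assessment that shows it.

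**The concern.** A site that follows the MRI note in 10.3.1.2 and takes a chest X-ray has done what that section allows. It has also departed from 9.12 and from 9.14.1.

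The choice bears on the endpoint because the protocol's own measurability threshold in the lung is twice as large by X-ray as by CT. In a patient whose chest is followed by X-ray, a small lung lesion cannot be a target lesion and its growth does not enter the sum of diameters. Progression in the lung may then be recognised at a later assessment than it would have been on CT, and the PFS date moves with it.

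Two features of the plan make this hard to repair afterwards. Under Section 10.3.1.3 the core laboratory holds all scans in case the sponsor wants PFS confirmed, but a chest CT that was never acquired cannot be re-read. And none of the five sensitivity analyses in SAP Table 2 concerns imaging modality. An X-ray assessment counts as done, so the rules for missed visits do not pick it up.

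**Working it through.** **1. The chest-imaging rules side by side**

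| Place | Patients covered | Chest imaging | X-ray allowed? |
|---|---|---|---|
| 10.3.1.2, MRI note | imaged by MRI | non-contrast CT or digital X-ray | yes |
| 9.12 | contrast CT contraindicated | non-contrast CT, mandatory (plus MRI) | no |
| 9.14.1 | patients generally | CT at every tumor assessment | no |
| 10.3.1.2, CT bullet | contrast hypersensitivity on study | non-contrast CT, described as acceptable | not named |

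The MRI rules in 10.3.1.2 apply when IV contrast is medically contraindicated, so they concern the same patients as 9.12. The first row contradicts the second and third. The fourth is permissive in wording, so the first row does not fit it rather than flatly contradicting it.

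**2. What the thresholds imply**

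Inputs from 10.3.1.1: 10 mm by CT or MRI, 20 mm by chest X-ray. A lung lesion from 10 mm up to just under 20 mm is measurable on CT and not on X-ray.

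Appendix 4 sets irPD at an increase in tumor burden of at least 20% and at least 5 mm over nadir. A sole lung target growing from 10 to 15 mm (+5 mm; 5/10 = +50%) meets that size rule. It stays below 20 mm throughout, so on X-ray it would never have been a target. This example uses the irRECIST rule, which serves a secondary endpoint. The measurability gap itself applies equally to RECIST 1.1 targets.

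**3. Size of a delay in one patient**

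Inputs: scans every 6 weeks to week 36; 30.4375 days per month (SAP 6.1); control median of 4 months (13.1.2). Detection one scan late shifts the date by 42 / 30.4375 = 1.38 months, and 1.38 / 4 = 34% of the control median.

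**4. Does it matter for the trial's test?**

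First, the plan's event number (HR 0.57, one-sided alpha 0.10, power 80%, 1:1):

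- Schoenfeld: (1.2816 + 0.8416)² / (0.25 × (ln 0.57)²) = 4.508 / 0.0790 = 57.1, so 58 events.
- Freedman: 4.508 × (1.57 / 0.43)² = 60.1, so 61 events.
- Power at 60 events (Schoenfeld): 81.5%.

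The planned 60 events are reproduced to within 2 and are not in dispute.

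Next, a simulation with 35 patients per arm, exponential medians of 4 and 7 months and uniform accrual over 9 months. Every event is dated at the next scheduled scan (6-weekly, then 9-weekly). Data are cut at the 60th event, and the test is a single unstratified log-rank test at one-sided 0.10, with 1,500 runs per row. The documents give no delay rate, so the share found late is **assumed**, and it is taken as equal in both arms.

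| Share found late | Scans late | Power | Control median as detected (months) |
|---|---|---|---|
| 0% | 0 | 0.81 | 4.7 |
| 2% | 1 | 0.78 | 4.9 |
| 5% | 1 | 0.81 | 4.9 |
| 5% | 2 | 0.81 | 5.0 |
| 10% | 1 | 0.79 | 4.9 |
| 10% | 2 | 0.82 | 5.1 |
| 30% (extreme) | 2 | 0.80 | 5.7 |

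The Monte Carlo standard error is √(0.8 × 0.2 / 1500) = 0.01. The differences in power show no trend with the amount of delay. The 4.7 in the first row exceeds 4 because progression is dated at a scheduled scan. What moves is the PFS date, not the power of the comparison. The simulation cannot speak to bias between arms, because it assumes equal delay.

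**The case against.** The strongest reply is that the rest of the protocol already protects the chest assessment. Section 9.12 makes non-contrast CT mandatory, 9.14.1 has CT at every assessment, 10.3.1.1 prefers CT even without contrast, and 10.3 requires each lesion to be followed by its screening method, naming only CT and MRI. On this view the X-ray option is a loose phrase with no demonstrated effect. Much of that stands, and it rules out several stronger readings.

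- **A reader might infer that lung progression is missed.** The 10 and 20 mm figures define measurable disease. They are not the smallest visible lesion, nor the size a new lesion needs to count as progression. Non-measurable lesions are also followed. A volume ratio built from the two thresholds would not estimate delay either.
- **A reader might infer that a patient who develops contrast allergy moves from CT to X-ray.** The hypersensitivity bullet sends that patient to non-contrast chest CT, and 10.3 keeps the screening method.
- **A reader might infer that with 60 events a few misdated patients change the result.** The simulation shows no clear power loss. Phase 2 is double-blind, so there is no reason to expect delay to fall on one arm.
- **A reader might want pelvic MRI aligned with 9.12.** Section 10.3.1.2 images the pelvis only when clinically indicated in CT patients too, so that change would create a new mismatch.

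What the reply does not remove is the contradiction. The MRI note offers X-ray without restriction. The same-method rule helps with lesions already followed on CT, but not with a patient whose chest is imaged by X-ray from the start.

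**Conclusion.** The point holds as a contradiction with a possible, limited effect on the primary endpoint. Section 10.3.1.2 permits a chest X-ray where 9.12 and 9.14.1 call for chest CT. In a patient followed that way, a 10–19 mm lung lesion is not measurable by the protocol's own definition, and lung progression may be dated later, by 1.38 months for each 6-week scan of delay.

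The number of patients is not in the documents. If 3% to 10% of the 70 had a contrast contraindication (an assumption), that would be 2 to 7 patients. Those who actually have X-ray and progress first in the lung would be only some of these, possibly none. No loss of power and no bias between arms is shown. The case for changing the text rests on the conflict between sections, the avoidable weakening of lung assessment for PFS and pulmonary monitoring, and the ease of the correction.

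**What to change.** Reconcile Sections 9.12, 9.14.1 and both parts of 10.3.1.2 by deleting the digital chest X-ray alternative from the MRI note in 10.3.1.2. A non-contrast chest CT then accompanies the MRI at every tumor assessment. No change to the pelvic field is needed.

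The cost is a short protocol edit and, for a few patients, a non-contrast CT in place of an X-ray. It adds no new procedure, since 9.12 already requires that CT and 10.3.1.2 already accepts it. The sample size and the analysis methods are unaffected.
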